## 7.2.5 Sponsor Responsibility for Reporting Adverse Events

All Adverse Events will be reported to regulatory authorities, IRBs and investigators in accordance with all applicable global laws and regulations.

#### 8.0 STATISTICAL ANALYSIS PLAN

## 8.1 Statistical Analysis Plan Summary

The phase I dose escalation will utilize the modified continuous reassessment method (mCRM) to identify the MTD. A "pick-the-winner" design for the randomized phase II clinical trial is proposed by employing Simon minimax two-stage design and Bayesian posterior probability. This design will have an 86% overall power to claim arm B as the winner when the true probabilities of response with arms A and B are 18% and 38%, respectively. The power slightly deceases to 75% when the response rate is 23% in arm A with 38% in arm B. The power is 57% when there is only 10% difference of response rate (arm A: 28%; arm B: 38%). The type I error is controlled at 16%.

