#### 8.2.6 Sample size calculation and Interim Analysis.

From historical data(Edward B Garon, 2014) (Socinski, Checkmate 026, EMSO 2016; Hellman et al, Keynote 001, WCLC, 2015; ), we will consider 25% response rate as not warranting further study. We will use 45% response rate as a promising result to pursue further study. In other words, we are interested in at least 20% (45% vs. 25%) improvement in treatment efficacy for arms B versus A. For each arm, using a Simon Mini-Max two-stage design with 10% type I error rate and 10% type II error rate, 23 patients will be enrolled in the first stage of the trial. If 5 or fewer patients respond, the treatment will be stopped. If 6 or more patients show a response, 16 additional patients (a total of 39 patients per group) will be enrolled. If the total number responding is 13 or less, we will conclude that the treatment is not effective. A total sample size will be 78 patinets if both arms finish the 2nd stage. If both arms fail at the first or second stage, the trial will stop. No winner will be claimed. The sample size will be 46 if both arms fail at the first stage and 62 if only one arm fails at the first stage. If only one arm pass the second stage, the arm will be the winner. If both arms pass the second stage, we will use the posterior probability, Pr(B > A), (probability of the response rate in arm B higher than in arm A) to select the winner. A non-informative prior of beta distribution, beta(1,1) in both arms will be used to calculate the posterior probability. Arm B will be claimed as the winner if  $Pr(B > A) > \delta = 0.8$ .

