#### 8.4 Power Analysis

Power: Assuming that the true probabilities of response in arms B and A are 45% and 25%, respectively (scenario 1: 20% difference of response rate), the overall probability (power) of correctly choosing arm B as superior is 87% on the basis of superiority shown at the end of the trial. The probability of stopping arm A early and declaring arm B superior at the end of the trial is 83%. There are 7% of both arms passing the second stage with 3% claiming arm B as the winner by the Bayesian posterior probability. In a 15% difference of response rate, the overall power is 69% and 77% for the comparison of arms B and A with 40% versus 25% (scenario 2) and 45% versus 30% (scenario 3), respectively. Proportion of both arms passing the 2nd stage is 6% in scenario 2 (scenario 3: 22%), with 2% (scenario 3: 9%) claiming arm B as the winner by the Bayesian posterior probability.

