#### 8.5 Type I error

Type I error: In the null hypothesis of a 25% response rate in both arms, there are 8% misclassifying arm B as winner (i.e., 8% type I error). Among them, only 1% has both arms passing the 2nd stage, and less than 0.01% misclassify arm B as winner.

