#### 8.6 Summary

Summary: With  $\delta$ =0.8, the design has a 87% power to detect a 20% difference of response rate. The power decreases to a range of 69-77% to differentiate a 15% difference of response rate. The type I error is controlled at 8% when both arms have a 25% response rate.

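### Section 8.1 states 86% and 75% phase II power where the rule in 8.2.6 gives 65.5% and 63.4%; its 16% type I error is undefined, and the 83% early-stopping figure in 8.4 should be 43%

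*Combined protocol and SAP*

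**What the plan says.** Section 8.1 summarises the phase II performance at a fixed 38% response rate in arm B. It states "This design will have an 86% overall power to claim arm B as the winner" when arm A is at 18%, then "The power slightly deceases to 75% when the response rate is 23% in arm A with 38% in arm B", then 57% at 28% versus 38%. It closes with "The type I error is controlled at 16"%, giving neither the null response rate nor the event counted as an error.

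Section 8.2.6 sets the rule on different rates: "we will consider 25% response rate as not warranting further study", with 45% as promising. Each arm follows a Simon minimax design with 10% type I and 10% type II error. The first stage has 23 patients and stops the arm at 5 or fewer responses. The second brings the arm to 39, where "If the total number responding is 13 or less, we will conclude that the treatment is not effective". If one arm passes, it wins. If both pass, arm B wins when the posterior probability that its rate is higher exceeds 0.8, under beta(1,1) priors; Table 14 names arm A when that probability is below 20%.

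Sections 8.4 to 8.7 report this design's performance: power of 87% (45% vs 25%), 69% (40% vs 25%) and 77% (45% vs 30%). Section 8.4 adds, for the first case: "The probability of stopping arm A early and declaring arm B superior at the end of the trial is 83"%. Section 8.5 says "there are 8% misclassifying arm B as winner (i.e., 8% type I error"), for 25% in both arms, and 8.6 repeats it: "The type I error is controlled at 8% when both arms have a 25% response rate".

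**The concern.** Sections 8.1 and 8.4–8.6 describe one trial at different response rates with different type I errors, and the documents contain only one rule. That rule was sized to accept an arm at 45%, so at 38% arm B should often fail it. A power of 86% there looked too high.

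The 16% and the 8% differ by a factor of two, and the reader is not told whether they measure the same thing. The 83% also does not look like an early-stopping probability beside the table in 8.7.

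A reader who uses only the summary would believe that the trial will very probably identify the combination if it raises response from 18% to 38%. A reader of 8.4 would expect arm A to close at the interim, with arm B going on to win, in about five trials out of six.

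**Working it through.** **Inputs.** From 8.2.6: 5/23 then 13/39 in each arm, beta(1,1) priors, threshold 0.8. From Table 14: the 20% threshold for arm A. From 8.1, 8.4 and 8.5: the response rates and the stated results. All probabilities below are exact binomial sums, not simulations.

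**Formulas.** For an arm with response rate p, let X ~ Bin(23, p) and Y ~ Bin(16, p).

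- F1(p) = P(X ≤ 5): fails at stage 1.
- F2(p) = P(X ≥ 6 and X + Y ≤ 13): fails at stage 2.
- Pass(p) = 1 − F1 − F2.

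The arms are independent, so

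P(B wins) = F1(pA)·Pass(pB) + F2(pA)·Pass(pB) + P(both pass and Pr(B > A) > 0.8).

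It follows that P(B wins) ≤ Pass(pB), whatever the posterior threshold.

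**Step 1: check against 8.2.6 and 8.4–8.7.** A search for the minimax design at 25% vs 45% with 10%/10% errors returns 5/23, 13/39, with Pass(0.25) = 0.0845 and Pass(0.45) = 0.9009. The winner probabilities are:

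| A vs B | Quantity | Exact | Stated |
|---|---|---|---|
| 25% vs 45% | B wins | 85.8% | 87% |
| 25% vs 40% | B wins | 69.9% | 69% |
| 30% vs 45% | B wins | 76.1% | 77% |
| 25% vs 25% | B wins | 7.75% | 8% (8.06% in 8.7) |

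All agree to within about 1.5 points, so 8.4–8.7 describe the rule in 8.2.6.

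**Step 2: the same rule at the rates in 8.1.** Pass(0.38) = 0.6579, which is the ceiling on power in every row.

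| A vs B | A fails stage 1, B passes | A fails stage 2, B passes | Both pass, B chosen | Sum | Stated |
|---|---|---|---|---|---|
| 18% vs 38% | 0.5118 | 0.1422 | 0.0009 | 0.6549 | 86% |
| 23% vs 38% | 0.3679 | 0.2596 | 0.0065 | 0.6340 | 75% |
| 28% vs 38% | 0.2252 | 0.3179 | 0.0213 | 0.5644 | 57% |

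The first two stated powers exceed the 65.8% ceiling, by 86 − 65.8 = 20.2 and 75 − 65.8 = 9.2 points. Against the exact powers the gaps are 86 − 65.5 = 20.5 and 75 − 63.4 = 11.6 points. The third figure is acceptable.

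**Step 3: type I error.** At 25% in both arms, arm B wrongly wins with probability 0.0775. By symmetry arm A does too, so either arm wrongly wins with probability 0.1551. The 8% in 8.5 and 8.6 is the first quantity. The 16% in 8.1 is close to the second, but the text does not say so. The only control rates named in 8.1 are 18%, 23% and 28%. With both arms at 18%, the either-arm probability under this rule is only 0.0118.

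**Step 4: the 83% in 8.4.** At 25% vs 45%, F1(0.25) = 0.4685.

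- A fails stage 1 and B passes: 0.4685 × 0.9009 = 0.4220 (8.7 table: 0.43).
- A fails stage 2 and B passes: 0.4027 (8.7 table: 0.41).
- Sum: 0.8247, which matches the 83%.
- Both pass and B is chosen: 0.0337 (8.7: 3.05%).

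The 83% is therefore arm A failing at either stage. An arm that fails stage 2 has enrolled all 39 patients and has not been stopped early. The difference is 83 − 43 = 40 points.

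**Possible source of the 8.1 powers (inference only).** A minimax design for 18% vs 38% at 10%/10% is 3/20, 9/35. With threshold 0.8 it gives 85.9%, 75.1% and 57.4%, matching all three stated powers. It appears nowhere in the documents and would need 2 × 35 = 70 patients, not 78. The conclusion does not rest on it.

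**The case against.** The strongest reply is that the operative sections are right. Sections 8.2.6 and 8.4–8.7 give the rule, its powers and a defined type I error, and the 78 patients in the trial summary agree with them. On this view 8.1 is stale summary text that drives no decision. That is true and limits the consequence, but 8.1 is in force as the summary of the analysis plan, and two of its powers cannot be reached under the rule.

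On type I error, 16% and 8% can both be true of this design, as either arm and arm B only. This stands: the 16% is not shown to be wrong. The defect is the missing definition.

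On the 83%, the paragraph in 8.4 can be read as splitting the 87% into arm A dropping out and the Bayesian comparison deciding. The plan also says elsewhere that the trial stops if both arms fail at either stage, and 8.7 prints the two cells separately. This reading explains where the number comes from, and it favours relabelling: 43% plus 3% would no longer account for the 87%. It does not rescue the word early.

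A last point concerns the remedy. With 10,000 simulations the standard error at 87% is about 0.35 points, so 87% lies somewhat above the exact 85.8%. The plan should use one set of figures throughout.

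**Conclusion.** The concern holds. Under the only phase II rule in the documents, power is 65.5% at 18% vs 38% (stated 86%) and 63.4% at 23% vs 38% (stated 75%); 56.4% at 28% vs 38% agrees with the stated 57%. The 16% type I error lacks a null rate and an error event. The 83% in 8.4 is the probability that arm A fails at either stage and arm B passes; stopping arm A at stage 1 with arm B passing has probability 42.2% exactly, 0.43 in the plan's own table.

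The calculation assumes independent binomial responses, full enrolment at each stage and the thresholds as written. The ceiling of 65.8% depends on neither the prior nor the posterior threshold. The error is in what the plan reports about its own performance, not in its size or decision rules. It should be fixed.

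**What to change.** - **Section 8.1, power.** Replace the three powers with those of the 25%/45% design, naming the rates: 45% vs 25%, 40% vs 25% and 45% vs 30%. Use the same set of values in 8.1, 8.4, 8.6 and 8.7, either the simulated 87%, 69% and 77% or, better, the exact 85.8%, 69.9% and 76.1%.
- **Sections 8.1, 8.5 and 8.6, type I error.** State the null rate (25% in both arms) and the error event, and use one definition. Keeping the definition in 8.5 (arm B wrongly wins, about 8%) needs the least change. If the either-arm probability (about 16%) is also wanted, give it beside the first with its own label.
- **Section 8.4.** Preferably keep 83% and describe it as arm A failing at stage 1 or stage 2 with arm B passing, which preserves the split of the 87%. Otherwise give 43% for stopping arm A at stage 1.

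The cost is a text correction. Sample size, cut-offs and the winner rule do not change. The stated power at the 8.1 rates is withdrawn, and if 43% replaces 83% the early-stopping figure becomes less favourable.

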## 8.2 Statistical Analysis Plan

#### 8.2.1 Phase I dose escalation.

The primary objective of this phase I dose escalation is to find a maximum tolerated dose (MTD) corresponding to a risk of DLT occurring in 30% of patients. Two dose levels have been identified for experimentation (200mg PO daily and 400mg PO daily) with a back-up dose at 100mg PO daily, and due to safety concerns the first cohort of patients will receive the lowest dose (200mg). The study uses the modified continuous reassessment method (mCRM) described later to design dose escalation (O'Quigley et al., 1990). The design will recruit patients in cohorts of three patients each and will not allow for dose-skipping during escalation. A total of 12 patients will be enrolled for the Phase I dose escalation. The initial guess of the risk of DLT at the lowest dose (200mg) is 10% whilst the best guess of the MTD is at dose level 2 (400mg) (i.e., a 30% risk of DLT at this dose level). The initial guesses of risk of DLT are established for each dose level as shown in Table 10.

Table 10. Initial estimates of the probability of DLT at each dose level.

	Dose cohort		
	100mg PO Daily	200mg PO Daily	
	(back-up dose)	(starting dose)	400mg PO Daily
initial guessed DLT probability	1%	10%	30%

## 8.2.2 Definitions for Dose Limiting Toxicities.

The period for evaluating DLTs is defined as the time period starting with the first dose of investigational products until the planned administration of the second dose of pembrolizumab. Subjects are considered evaluable for assessment of DLTs if they receive at least 75% of the protocol assigned doses of both pembrolizumab and vorinostat and complete the safety follow-up through the end of the DLT evaluation period, or experience a DLT during the DLT evaluation period.

Subjects who do not remain on the study up to this time for reasons other than DLT will be replaced with another subject at the same dose level. DLTs will be graded according to the National Cancer Institute Common Terminology Criteria for Adverse Events (NCI CTCAE v4.03). A DLT will be defined as any Grade 3 or higher toxicity that occurs during the DLT evaluation period. Toxicity that is clearly and directly related to the primary disease or to another etiology is excluded from this definition.

#### The following will be DLTs:

- Any Grade 4 immune-related adverse event (irAE)
- Any ≥ Grade 3 colitis
- Any Grade 3 or 4 non-infectious pneumonitis irrespective of duration
- Any Grade 2 pneumonitis that does not resolve to ≤ Grade 1 within 3 days of the initiation of maximal supportive care
- Any Grade 3 irAE, excluding colitis or pneumonitis, that does not downgrade to Grade 2 within 3 days after onset of the event despite optimal medical management including systemic corticosteroids or does not downgrade to ≤ Grade 1 or baseline within 14 days
- Liver transaminase elevation > 8 × upper limit of normal (ULN) or total bilirubin > 5 × ULN
- Any ≥ Grade 3 non-irAE, except for the exclusions listed below

#### The definition excludes the following conditions:

- Grade 3 fatigue lasting ≤ 7 days
- Grade 3 endocrine disorder (thyroid, pituitary, and/or adrenal insufficiency) that is managed with or without systemic corticosteroid therapy and/or hormone replacement therapy and the subject is asymptomatic
- Grade 3 inflammatory reaction attributed to a local antitumor response (eg, inflammatory reaction at sites of metastatic disease/lymph nodes)
- Concurrent vitiligo or alopecia of any AE grade
- Grade 3 infusion-related reaction (first occurrence and in the absence of steroid prophylaxis) that resolves within 6 hours with appropriate clinical management
- Grade 3 or 4 neutropenia that is not associated with fever or systemic infection that improves by at least 1 grade within 3 days. Grade 3 or Grade 4 febrile neutropenia will be a DLT regardless of duration or reversibility
- Grade 3 or 4 lymphopenia
- Grade 3 thrombocytopenia that is not associated with clinically significant bleeding that requires medical intervention, and improves by at least 1 grade within 3 days

- Isolated Grade 3 electrolyte abnormalities that are not associated with clinical signs or symptoms and are reversed with appropriate maximal medical intervention within 3 days
- Grade 3 amylase or lipase abnormality that is not associated with symptoms or clinical manifestations of pancreatitis
- Immune-related AEs are defined as AEs of an immune nature (ie, inflammatory) in the
  absence of a clear alternative etiology. In the absence of a clinically significant
  abnormality, repeat laboratory testing will be conducted to confirm significant
  laboratory findings prior to designation as a DLT. Laboratory abnormalities that are
  not deemed to be clinical significant will not be considered a DLT.

While the rules for adjudicating DLTs in the context of dose exploration are specified above, an AE not listed above may be defined as a DLT after a consultation with the sponsor and investigators, based on the emerging safety profile.

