### Vorinostat in Lung Cancer.

Suberoylanilide hydroxamic acid (SAHA, vorinostat) is an orally active, small molecule inhibitor of histone deacetylase (HDACi). Clinical trials have shown that daily oral vorinostat is safe and tolerable and has a broad range of clinical activity in advanced solid tumors.

Vansteenkiste et al. conducted a phase II trial of oral vorinostat in 16 patients with breast cancer (3 patients), NSCLC (10 patients), and colorectal cancer (3 patients). Patients were treated with oral vorinostat 200mg BID, 300mg BID, or 400mg BID for 14 days on, 7 days off on a 21-day cycle. Dose-limiting toxicities occurred in a total of 6 patients at both the 300mg BID and 400mg BID doses and included weight loss, asthenia, thrombocytopenia, nausea, vomiting, and anorexia. Grade 3/4 toxicities included thrombocytopenia (50%), anemia (12%), asthenia (12%), nausea (12%), and anorexia (6%). No dose limiting toxicities

[figure not shown]
occurred at the 200mg BID dose level. Although treatment duration was short and TTP was 33.5 days, 6/10 patients with NSCLC had a best response of stable disease by RECIST (Vansteenkiste et al., 2008). Kelly et al. conducted a phase I study that enrolled 50 patients with solid tumors and 23 patients with hematologic malignancies. The maximum tolerated dose was vorinostat 400mg daily or 200mg bid for continuous daily dosing and 300mg bid for 3 of 7 consecutive days. In addition to the dose-limiting toxicities outlined in the prior trial, one patient had elevation of liver enzymes. Only two patients with lung cancer were enrolled in that study; there were two patients with partial responses (laryngeal cancer and mesothelioma) (Kelly et al., 2005). Ma et al. studied vorinostat in a preclinical model with a window of opportunity trial in 15 patients with early-stage lung and esophageal cancers (Ma et al., 2013). Vorinostat 400mg daily was given for 2-9 days and patients had pre-therapy and post-therapy biopsies of target lesions. The study included 10 evaluable patients (8 with lung adenocarcinoma, one with lung squamous cell cancer, and one with esophageal adenocarcinoma). Eight of 9 lung cancer post-treatment biopsies exhibited either acute or chronic inflammation or necrosis when compared to pre-treatment biopsies. Additionally, there was evidence of CD8 positive tumor infiltrating lymphocytes in the post-treatment tissue, supporting the theory that vorinostat acts as a biologic effector of tumor immunogenicity.

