## **6.0 TRIAL FLOW CHART**

## 6.1 Study Flow Chart\*

Trial Period:		Treatment Cycles								End of Treatment	Post-Treatment		
	Study					To be		ated be	eyond		Safety		Survival
Treatment Cycle/Title:	Screening (Visit 1)	1	2	3	4	5	6	7	8	Discon	Follow- up	Follow Up Visits	Follow- Up
Scheduling Window (Days):	-27 to c1d1 e		± 7	± 7	± 7	± 7	± 7	± 7	± 7	At time of Discon	30 days post last dose of study drug	Every 8 weeks post discon	Every 12 weeks
Screening Consent	Χ												
Informed Consent	Х												
Inclusion/Exclusion Criteria	Х												
Demographics and Medical History	Х												
Prior and Concomitant Medication Review	Х	Х	Х	х	Х	Х	х	Х	Х				
Vorinostat compliance review/Pill Diary		Х	Х	х	Х	Х	Х	Х	Х	Х			
Trial Treatment Administration		Х	Х	Х	Х	Х	Х	Х	Х				
Post-study anticancer therapy status										×	Х		Х
Survival Status		Х	Х	Х	Х	Х	Х	Х	Х	Х			Х
Review Adverse Events	Χ †	Х	Х	Х	Х	Х	Х	Х	Х	Х	Х		
Full Physical Examination	Х												
Directed Physical Examination		Х	Х	Х	Х	Х	Х	Х	Х	Х	Х		
Vital Signs and Weight	Х	Х	Х	Х	Х	Х	Х	Х	Х	Х	Х		
ECOG Performance Status	Х	Х	Х	Х	Х	Х	Х	Х	Х		Х		
Pregnancy Test – Urine or Serum b-HCG	Х	Х	Х	Х	Х	Х	Х	Х	Х		Х		

Trial Period:					Cycle	es				End of Treatment	Post-Treatment		
	Study					To be		ated be	eyond		Safety		Survival
Treatment Cycle/Title:	Screening (Visit 1)	1	2	3	4	5	6	7	8	Discon	Follow- up	Follow Up Visits	Follow- Up
Scheduling Window (Days):	-27 to c1d1 e		± 7	±7	± 7	±7	± 7	± 7	± 7	At time of Discon	30 days post last dose of study drug	Every 8 weeks post discon	Every 12 weeks
PT/INR and aPTT	Х	X (C1D15 -C1D21											
CBC with Differential	Х	Х	Х	Х	Х	Х	Х	Х	Х		Х		
Comprehensive Serum Chemistry Panel	Х	Х	Х	х	Х	Х	Х	Х	Х	Х	Х		
Magnesium	Х	Х	Х	Х	Х	Х	Х	Х	Х	Х	Х		
Urinalysis	Х												
T3, FT4 and TSH	Х	Х	Х	Х	Х	Х	Х	Х	Х	Х	Х		
Echocardiogram g	Х												
EKG	Х												
Tumor Imaging (CT Thorax/Abdomen)	Х			Х		Х		Х		Х		X d	
Brain MRI or Brain CT	Х												
Archival or Newly Obtained Tissue Collection a,b	Х	X (C1D15 -C1D21											
Correlative Studies Blood Collection c	X c	X c		Х		Х		Х		Х		Х	

Trial Period:		Treatment Cycles						End of Treatment	Po	st-Treatme	nt		
	Study					To be		ated be	yond		Safety		Survival
Treatment Cycle/Title:	Screening (Visit 1)		2	3	4	5	6	7	8	Discon		Follow Up Visits	Follow- Up

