Scheduling Window (Days):	-27 to c1d1 e		± 7	± 7	± 7	± 7	± 7	± 7	± 7	At time of Discon	30 days post last dose of study drug	Every 8 weeks post discon	Every 12 weeks

\*All clinic visits and tests (including labs, imaging studies and biopsies) will have a plus or minus 7 day window for completion.

<sup>a All patients in the study are required to have a pre-treatment biopsy, where feasible, or archival tissue from after the most recent line of therapy, which will be tested for PD-L1 and nanostring analyses.

<sup>b C1D15-21 biopsies will be done on patients in the phase I dose escalation, phase Ib and phase II parts of the study, where feasible. PD-L1 and Nanostring studies will be completed on all of these biopsy specimens.

<sup>c Timepoints for the first two correlative study blood collection include first during Screening or on C1D1, and second on C1D15. The remainder of the blood collections will occur with the reimaging scans. Histone acetylation studies will be run on serial PBMC draws in all patients (includes phase I dose escalation, phase Ib expansion and phase II). The blood will be collected in five 10 mL green top (sodium heparin) tubes for a total of about 50mL of whole blood.

<sup>d Subjects who discontinue trial treatment for a reason other than disease progression will move into the Follow-Up Phase and should be assessed every 8 weeks (56 ± 7 days) by radiologic imaging to monitor disease status. After 1 year, the imaging time point will occur every 12 weeks (± 7 days).

<sup>e The main study screening window will occur within 28 days prior to the first study treatment. Note additionally that screening laboratory blood and urine studies must be obtained within 10 days of C1D1, with the exception of pregnancy testing in applicable patients, which must be obtained within 72 hours of first treatment.

f Only serious adverse events will be collected during the screening window.

<sup>9 Echocardiogram will be performed at screening for baseline, and may be repeated if clinically indicated per the treating investigator. Echocardiogram should be performed within 30 days of treatment initiation.

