**Table 9. Laboratory Tests** 

Hematology	Chemistry	Urinalysis	Other
Hematocrit	Albumin	Blood	Serum β-human chorionic gonadotropin†
Hemoglobin	Alkaline phosphatase	Glucose	(β-hCG)†
7.1.5.1.1 Pplatelet count	Alanine aminotransferase (ALT)	Protein	PT (INR)
WBC (total and differential)	Aspartate aminotransferase (AST)	Specific gravity	aPTT
Red Blood Cell Count		Microscopic exam (If abnormal)	Total thriiodothyronine (T3)
Absolute Neutrophil Count	Carbon Dioxide ‡	results are noted	Free tyroxine (T4)
Absolute Lymphocyte Count	(CO 2 or biocarbonate)	Urine pregnancy test †	Thyroid stimulating hormone (TSH)
	Calcium		
	Chloride		Blood for correlative studies
	Glucose		
	Potassium		
	Sodium		
	Magnesium		
	Total Bilirubin		
	Direct Bilirubin (If total bilirubin is elevated above the upper limit of normal)		
	Total protein		
	Blood Urea Nitrogen		

† Perform on women of childbearing potential only. If urine pregnancy results cannot be confirmed as negative, a serum pregnancy test will be required. ‡ If considered standard of care in your region.

Laboratory tests for screening or entry into the Second Course Phase should be performed within 10 days prior to the first dose of treatment. Any screening labs done within 7 days of C1D1 do not need to be repeated prior to first treatment. After Cycle 1, pre-dose laboratory procedures can be conducted up to 72 hours prior to dosing. Results must be reviewed by the investigator or qualified designee and found to be acceptable prior to each dose of trial treatment.

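### No blood count or chemistry is scheduled between C1D1 and the C2D1 pre-dose draw, so the 3-day DLT exemptions cannot be applied systematically from scheduled data

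*Combined protocol and SAP*

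**What the plan says.** **DLT rules (8.2.2, exclusions).** Three laboratory exemptions depend on change within three days. The platelet exemption is "Grade 3 thrombocytopenia that is not associated with clinically significant bleeding that requires medical intervention, and improves by at least 1 grade within 3 days". The neutrophil exemption is "Grade 3 or 4 neutropenia that is not associated with fever or systemic infection that improves by at least 1 grade within 3 days". An isolated, symptom-free Grade 3 electrolyte abnormality is exempt if it is reversed within the same interval. Section 8.2.3 sets the DLT window at the first 21 days; 8.2.2 runs it to the planned second pembrolizumab dose.

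**Schedule (6.1).** The row "CBC with Differential" has one entry at screening and one per cycle. Chemistry and magnesium follow the same pattern. Section 5.2.2 places flow-chart procedures before Day 1 dosing, so these entries mean C1D1 and C2D1. By contrast, "PT/INR and aPTT" carries an explicit C1D15-C1D21 entry, as does tissue collection. Footnote c sets a C1D15 blood draw, for correlative studies only.

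**Laboratory timing.** The note to Table 9 (7.1.5) says "Any screening labs done within 7 days of C1D1 do not need to be repeated prior to first treatment", and then "After Cycle 1, pre-dose laboratory procedures can be conducted up to 72 hours prior to dosing". The flow-chart footnote says "All clinic visits and tests (including labs, imaging studies and biopsies) will have a plus or minus 7 day window for completion".

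**Expected toxicity (4.2.1).** The background attributes cytopenias to vorinostat. It cites a trial with Grade 3/4 thrombocytopenia in 50% of patients, at 200-400 mg twice daily, 14 days on and 7 off.

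**The concern.** A rule that turns on three-day change needs an observed onset and an observed recovery. The schedule has one count before treatment, which may be up to 7 days old, and one at the end of the window. Grade 4 thrombocytopenia has no exemption at all, so it should count however briefly it lasts, yet it too could arise and resolve between the two draws.

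The MTD comes from 12 patients' cycle 1 DLTs and is carried into phases Ib and II. If the DLTs that go unrecorded are mainly those the combination is expected to cause, the error runs in one direction, towards too high a dose. There is a secondary point about the on-treatment biopsy. It falls at C1D15-21, when everyone except Arm A is on continuous daily vorinostat, and the bleeding tests scheduled for those days leave out the platelet count.

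**Working it through.** **1. Count the draws.** Scheduled count or chemistry samples strictly between C1D1 and the C2D1 pre-dose draw: 0. The nominal gap is 22 − 1 = 21 days. With the stated windows it ranges from (22 − 7 − 3) − 1 = 11 days to (22 + 7) − (1 − 7) = 35 days. The windows move a draw but do not add one. If the C2D1 sample shows a Grade 3 value, its onset is undated and any recheck falls at or after the end of the window.

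**2. What one end-of-window sample can see.** The documents give no episode duration, so this is an assumption with a range. Let onset be uniform over days 2-21 (20 days), with a single draw at day 19 (72 hours early) or day 22. The probability of detection is the number of onset days whose episode covers the draw, divided by 20.

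| Duration | Draw at day 19 | Draw at day 22 |
|---|---|---|
| 3 days | 3/20 = 0.15 | 2/20 = 0.10 |
| 7 days | 7/20 = 0.35 | 6/20 = 0.30 |
| 14 days | 14/20 = 0.70 | 13/20 = 0.65 |

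One-third to two-thirds is therefore a fair working range for episodes of 7 to 14 days.

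**3. Reproduce the plan's mCRM.** The model is the one written in 8.2.3: logistic with intercept 3, Gamma(1,1) prior, standardized doses back-solved from the 1/10/30% skeleton, cohorts of 3, n = 12. With 20,000 simulated trials and the posterior mean of θ plugged in, 400 mg is selected in 83.2% of Scenario 1 trials (Table 13: 83.3%) and 25.7% of Scenario 3 trials (Table 13: 25.1%). The simulation is close enough to use.

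**4. Add under-detection.** Let f be the share of DLTs that are laboratory cytopenias (assumed 0.3-0.5) and d the fraction of those detected. Recorded rate = true rate × [1 − f(1 − d)]. In Scenario 3 (true rates 10/30/50%; 400 mg is above the MTD):

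- f = 0.3, d = 1/3: factor 0.80, recorded 8/24/40%
- f = 0.5, d = 1/3: factor 0.667, recorded 6.7/20/33.3%

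The chance of recording 0 of 3 at 200 mg, which sends the next cohort to 400 mg, rises from 0.70³ = 0.34 to 0.76³ = 0.44 and 0.80³ = 0.51.

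Selection of 400 mg in Scenario 3:

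| Variant | Full detection | d = 1/3 | d = 2/3 |
|---|---|---|---|
| Plug-in estimate | 25.7% | 45.4-60.2% | 35.0-41.8% |
| Posterior-mean toxicity | 20.6% | 39-55% | – |
| Plug-in, with the 8.2.3 drop to 100 mg after a DLT at 200 mg | – | about 40-54% | – |
| Posterior-mean, with that rule | – | about 36-50% | – |

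Across both estimators, with and without the de-escalation rule, and both detection fractions, the range is about 28-61%, against about 20-26% with full detection.

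**5. Where the effect disappears.** If cytopenias persist to C2D1, d approaches 1 and the bias is near zero. In Scenario 1, where 400 mg is the true MTD, the same under-detection at d = 1/3 raises correct selection from about 84% to 91-94%.

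**The case against.** **Testing outside the schedule.** A reader might infer that the three-day rules cannot be applied at all. The documents do not support that. Section 7.1 permits unscheduled procedures, 7.1.4.1 permits more frequent adverse event assessment, and 8.2.2 calls for repeat laboratory testing before a DLT is designated. An event found that way, or at C2D1, can be rechecked and classified. What stands is that these provisions act only after suspicion or after an abnormal result. The repeat testing has no stated timing, and a silent cytopenia raises no suspicion.

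**Silent abnormalities may not be DLTs.** Section 8.2.2 ends by excluding laboratory findings not deemed clinically significant. Section 7.2 treats values that cause no symptoms and need no therapy as not significant. Some unseen nadirs would therefore arguably not count, and the simulation, which treats every one as a missed DLT, overstates the loss to that extent. But 8.2.2 also gives numerical grade-and-duration rules for these very abnormalities, and significance cannot be judged on a value nobody has measured.

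**The size is assumption-driven.** This is correct. Nothing in the documents supports the 30-50% share, detection outside scheduled draws is set to zero, and continuous daily dosing could produce longer episodes. The background also tempers the 50% figure: it comes from 16 patients on a different schedule, no DLTs occurred at 200 mg twice daily, and a separate phase I study found a continuous-dosing MTD of 400 mg daily.

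**The 7-day window.** A reader might infer that the footnote lets a safety sample be drawn after the dose it should clear. It does not: the Table 9 note requires acceptable results before each dose, and 5.2.2 places dosing after the procedures. What is left is a mismatch in wording.

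**Biopsy.** A reader might infer that biopsies go ahead with no platelet count. The documents show only that none is scheduled; local pre-procedure practice is not described. Arm A takes no vorinostat.

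**Conclusion.** The concern holds in a limited form. The plan defines DLT exemptions by three-day change but schedules no count, chemistry or magnesium inside the cycle that could show it. The rules can still be applied to events that happen to be found, but not systematically from scheduled data. The direction of the resulting error is clear: unrecorded DLTs move the MTD upward. Its size is not established. The range of about 28-61% selection of 400 mg in Scenario 3, against about 20-26% with full detection, rests on the assumed share of laboratory DLTs and the assumed detection fraction. It should be read as showing sensitivity, not as a forecast. It shrinks to near zero if cytopenias last to C2D1, and it leads to no wrong dose choice in Scenario 1. The missing scheduled platelet count around the C1D15-21 biopsy is a real gap in the flow chart for patients on vorinostat. The laboratory window conflict is editorial.

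**What to change.** Reconcile 6.1 with 8.2.2 by adding blood count with differential, chemistry panel and magnesium to the C1D15 blood draw that footnote c already schedules. The DLT window then contains at least one scheduled mid-cycle safety sample, and a platelet count is available around the biopsy. Under the 7-day assumption, samples at days 15 and 22 catch 13/20 = 0.65 of episodes, about two-thirds, instead of about one-third. In the plug-in simulation this lowers selection of 400 mg in Scenario 3 from 45-60% to 35-42%.

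One mid-cycle sample does not by itself show a three-day change. The sponsor and investigators should decide whether the escalation part needs further draws, and when an abnormal result is rechecked so that the exemptions can be judged. Any condition on results before the biopsy is also theirs to set.

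Separately, word the 7-day footnote so that it agrees with the 72-hour pre-dose rule in 7.1.5.

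Cost: a flow-chart amendment and a tube or two at an existing draw. A few more DLTs may be recorded.
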